8.1 Sample Size Calculation

The sample size calculation is based on the primary efficacy endpoint "occurrence of treated relapse within 24 months after completion of the initial treatment". In the literature different information are given regarding the relapse rate for the control group receiving standard prednisone therapy. We have decided to assume a relapse rate of 51% according to Gipson et al. [8] which gives the worst case resulting in a conservative sample size estimation. The same rate is expected for the experimental group. If the relapse rate in the experimental group accounts to less than 15% above the relapse rate of the control group, this will be considered as clinically irrelevant based upon clinical judgment. Therefore the margin is set to δ =0.15. As the direction of the difference to be established is known for non-inferiority studies and as - due to the rareness of the disease and the related limited available number of patients - the study could otherwise not be performed with sufficient power, a one-sided significance level of 5% is applied. Testing at a one-sided significance level of α = 5% and aspiring a power of 80%, a total of 272 patients (136 per group) are required (calculations performed with AddPlan 6.0). To account for 10% drop-out rate and major protocol violations in a further 10% 340 patients will be randomized.

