8.2 Compliance/Rate of loss of follow up

The nephrotic syndrome in children is mostly an acutely presenting disease, and parents are very concerned about their child. With standard prednisone treatment we observe an adherence to therapy of more than 95%. According to our previous experience in performing studies in pediatric nephrology we assume that a minimum of 85% of patients assessed for eligibility will be allocated to study [4,5,19]. Due to the exclusive care of these patients in specialized pediatric nephrology centers we calculate with a loss of follow-up of maximum 20% which corresponds to our previous studies [4,5,19]. The recent study of the GPN, showing that MMF is efficacious in sustaining remission in children with frequently relapsing nephrotic syndrome, had only a drop-out rate of 4%. Therefore, for the entire study, we estimated 400 children with steroid-sensitive nephrotic syndrome to be assessed for eligibility, 340 to be allocated to study and 272 patients to be analyzed per protocol. However, in cases of premature withdrawal by a patient the persons having care and custody of this patient will be asked for informed consent so that routinely recorded data by the responsible physician can be used for the INTENT study. In this manner as many data as possible are recorded for evaluation of treatments in this rare disease.

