8.4 Statistical Methods

The primary efficacy endpoint is the occurrence of a treated relapse within 24 months after completion of initial treatment. The non-inferiority of the experimental group *vs.* control group will be evaluated using the test according to Farrington and Manning [17]. The one-sided significance level is set to 5%.

The hypotheses to be assessed in the primary efficacy analysis are formulated as follows: H_0 : $p_MMF - p_Prednisone \ge \delta$ (δ =0.15, non-inferiority margin, see Section 8.1 Sample Size Calculation for justification)

 H_1 : p_MMF – p_Prednisone < δ , where p_* denotes the relapse rate in the respective group.

Before database closure the assignment of patients to the PP population (patients with no major protocol violations) and the ITT population (as classified by the intent-to-treat principle) are defined in the statistical analysis plan. The confirmatory analysis is performed for both the PP population and the ITT population. This approach reflects the equal importance of both analysis sets in a non-inferiority trial [29]. For the PP analysis missing values for the primary endpoint are not expected. In the ITT population missing values will be replaced according to Higgins [27]. As appropriate, a third population will be defined to adequately incorporate routinely collected data of patients who withdraw prematurely but gave informed consent for usage of routinely collected data. Details on inclusion of such data into sensitivity analyses of primary and secondary endpoints will be defined in more detail in the SAP. In case of uncertainty regarding data quality and reliablility these patients will only be analysed descriptively.

Additionally, binary logistic regression models will be performed as sensitivity analysis for the intervention comparison of the relapse rates adjusting for age, gender, center (grouped), and for results of therapeutic drug monitoring (grouped) based on different populations (PP, ITT, with values of drop-outs set to worst case).

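### The worst-case rule for drop-outs in the section 8.4 sensitivity models is undefined by arm and, on its plain reading, anti-conservative for non-inferiority when drop-out is balanced

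*Protocol*

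**What the plan says.** Section 8.4 of the protocol defines a binary endpoint: "The primary efficacy endpoint is the occurrence of a treated relapse within 24 months after completion of initial treatment". The confirmatory analysis is a Farrington-Manning test of the MMF minus prednisone difference in relapse rate, run in both the PP and the ITT population. For ITT the section has a separate rule, imputation by a cited method. For PP it expects no missing primary outcomes.

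The worst-case rule comes afterwards, in a sentence on additional adjusted logistic regression models labelled as sensitivity analysis. They are to be run "based on different populations (PP, ITT, with values of drop-outs set to worst case". The protocol does not define worst case by arm, and it attaches no margin or decision rule to these models.

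Two other sections give the scale of missing data. Section 8.1: "To account for 10% drop-out rate and major protocol violations in a further 10% 340 patients will be randomized". Section 8.2: "we calculate with a loss of follow-up of maximum 20"%, next to a 4% drop-out rate in a recent trial of the same study group.

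**The concern.** Counting every drop-out as a failure is a familiar cautious choice in a superiority trial, because giving both arms the same value pulls their rates together. In a non-inferiority trial, pulling the rates together helps the claim. The natural reading of worst case for an unwanted event such as relapse therefore runs in the wrong direction here.

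The opposite reading, worst for the MMF claim, gives a very different analysis. The phrase covers both. At the planned 10% drop-out, with truly equal arms, the choice moves the pass rate of a margin test from 87% to 24%.

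What is at stake is the report, not the confirmatory result. A statement that the finding held under worst case could reassure readers without grounds. A statement that it failed could alarm them without grounds.

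**Working it through.** **Inputs**
- Control relapse rate: "We have decided to assume a relapse rate of 51"% (section 8.1).
- MMF relapse rate: "The same rate is expected for the experimental group" (section 8.1).
- Margin: "Therefore the margin is set to δ =0.15" (section 8.1).
- Level: "a one-sided significance level of 5% is applied" (section 8.1).
- 170 per arm (section 4.1).
- Drop-out of 4%, 10% or 20% (sections 8.1 and 8.2).
- My assumptions: drop-out is equal in the two arms unless stated, it is unrelated to relapse, and every drop-out has an unknown outcome.

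**The plan's own figure.** The Farrington-Manning sample size per arm is

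n = [1.645·√(p̃₁q̃₁ + p̃₂q̃₂) + 0.842·√(p₁q₁ + p₂q₂)]² / 0.15²

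with p₁ = p₂ = 0.51 and restricted estimates p̃₁ = 0.5846 and p̃₂ = 0.4346. This gives 135.3, so 136 per arm and 272 in total. Then 272 / 0.80 = 340. The plan's figures reproduce.

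**Formula for the check.** With drop-out fraction d and assigned value v (1 = relapse, 0 = none), the rate analysed in an arm is (1 − d)·p + d·v. The pass probability is the exact binomial probability that the Farrington-Manning test with margin 0.15 and one-sided 5% declares non-inferiority with 170 per arm. A hand check is Φ(−1.645 + (0.15 − Δ)/SE), where Δ is the difference analysed and SE = √[(p₁q₁ + p₂q₂)/170]. The test stands in for a decision that the logistic model does not make.

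**Reading A: relapse for every drop-out in both arms.** With equal d, Δ = (1 − d) × the true difference. The true rates are 0.66 and 0.51, so the null hypothesis holds.

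| Drop-out | Rates analysed | Δ | Hand check | Exact pass rate |
|---|---|---|---|---|
| 4% | 0.674 / 0.530 | 0.144 | 6.3% | 6.1% |
| 10% | 0.694 / 0.559 | 0.135 | 8.8% | 8.9% |
| 20% | 0.728 / 0.608 | 0.120 | 14.6% | 15.0% |

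Worked line at 10%: SE = √[(0.694·0.306 + 0.559·0.441)/170] = 0.0520; (0.15 − 0.135)/0.0520 = 0.289; Φ(−1.356) = 8.8%. If the number of drop-outs is held fixed, the pass rates are 5.9%, 8.0% and 13.3%. Analysing only completers gives 4.9% at 10% drop-out and 5.4% at 20%.

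With truly equal arms, reading A passes 87.4% and 88.3% of the time at 10% and 20% drop-out. Completers alone pass 83.4% and 80.1%. On this reading, the worst case is easier to pass than leaving the drop-outs out.

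**Reading B: MMF drop-outs relapse, prednisone drop-outs do not.** The true rates are 0.51 in both arms, so Δ = d.

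| Drop-out | Rates analysed | Δ | Hand check | Exact pass rate |
|---|---|---|---|---|
| 4% | 0.530 / 0.490 | 0.04 | 65.0% | 65.6% |
| 10% | 0.559 / 0.459 | 0.10 | 23.6% | 23.9% |
| 20% | 0.608 / 0.408 | 0.20 | 0.5% | 0.5% |

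At 10% drop-out, if MMF is truly 10 points better, reading B passes 83% of the time.

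**Limits of the two readings**
- Unbalanced drop-out: with 12% on MMF and 8% on prednisone, reading A turns a true 0.15 into 0.152 and passes 4.7% of the time. The dilution is then gone.
- An intermediate reading: with MMF drop-outs set to relapse and prednisone drop-outs at 51%, the pass rate at 10% drop-out is 59.3% under equality and 1.0% at the margin.

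**What a graded analysis would show.** Take 51% observed relapse in both arms and prednisone drop-outs imputed at 51%. At 4% and 10% drop-out, non-inferiority holds even if every MMF drop-out relapses. At 20%, each arm has 136 observed children and 34 drop-outs. The conclusion is lost at 28 relapses among the 34 MMF drop-outs: 97/170 against 86/170 gives z = −1.60, short of −1.645, whereas 27 relapses give z = −1.70.

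**The case against.** The strongest reply is that the percentages above are not error rates of this trial. The clause belongs to a supplementary logistic model with no margin. The confirmatory ITT test has its own imputation rule, PP carries equal weight, and section 8.4 leaves the use of routine data from withdrawn children, including a possible third population, to the SAP. The value assigned in each arm is also a detail that an SAP commonly settles. All of this stands, and it limits the point to a supportive analysis.

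The 20% case is an upper figure. Section 8.1 splits the loss from 340 to 272 into drop-out and protocol violations, and violators can keep their observed outcomes in ITT. A child who leaves after a treated relapse has already met the endpoint. This also stands, and the 4% and 10% rows are the more likely range.

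A reader might go further and infer that the worst-case analysis cannot test robustness at all, because it either favours MMF or condemns it. The documents do not support that. Passing the arm-specific version is strong evidence, the intermediate version separates equality from the margin, and the dilution under reading A needs roughly balanced drop-out.

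One part of the concern survives the reply. The protocol itself fixes a worst-case rule and does not merely stay silent. The plain meaning of that rule points the wrong way for this hypothesis, and an odds ratio without a margin cannot be read against 0.15 in any case.

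**Conclusion.** The point holds as a minor one. On its plain reading, the worst-case rule is anti-conservative for non-inferiority under balanced drop-out. A stand-in margin test would pass about 6%, 9% and 15% of the time at 4%, 10% and 20% drop-out when MMF is truly 15 points worse, against a nominal 5%. On the arm-specific reading the rule is a strict bound whose failure says little at 10% drop-out or more. The size rests on the planning rate of 51%, 170 per arm, drop-out that is equal by arm and unrelated to relapse, and the Farrington-Manning test standing in for the logistic model.

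It would be wrong to infer that the trial's type I error is inflated or that its main missing-data handling is faulty. The confirmatory PP and ITT analyses do not use this rule.

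**What to change.** In section 8.4, replace the worst-case clause for drop-outs with a tipping-point analysis on the risk difference in the ITT set:
- Impute prednisone drop-outs at the observed control relapse rate.
- Raise the relapse probability of MMF drop-outs in steps from that rate to 100%.
- Report the value, if any, at which the upper limit of the two-sided 90% interval reaches 0.15. This limit matches the one-sided 5% test.
- State that coding drop-outs as relapse in both arms is not evidence of robustness.

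The adjusted logistic models in PP and ITT can stay as planned. The cost is a few lines in the protocol and SAP and a short program. No new data are needed and the primary test does not change. The downside is a little more analysis work and a curve in place of one number.

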8.5 Interim Analyses

For the INTENT study, no interim analysis at a fixed time point is performed for the following reason: The recruitment phase is planned to be 36 months. The primary endpoint is occurrence of treated relapse within 24 months after end of initial treatment. Therefore, information on the primary endpoint for a first portion of the study patients will be available not before end of the recruitment phase. For this reason, a group-sequential approach was not pursued.

However, an independent DSMB will closely monitor the recruitment, the reported adverse events and the data quality of the study thus ensuring the ethical conduct of the study and protecting the safety interests of patients.

9 DATA MANAGEMENT

9.1 Data Management and Quality Assurance

The investigator or a designated representative must enter all protocol-required information in the electronic case report form (eCRF). The eCRF should be completed as soon as possible after the information is collected, preferably on the same day when a study subject is seen for an examination, treatment, or any other study procedure. The reason for missing data should be provided. The investigator is responsible for ensuring that all sections of the eCRF are completed correctly and that entries can be verified in accordance with the source data. Any entry and correction in the Remote Data Entry System will be documented automatically in an audit file.

Completeness, validity and plausibility of data will be checked in time of data entry (edit-checks) and using validating programs, which will generate queries. The investigator or the designated representatives are obliged to clarify or explain the queries. If no further corrections are to be made in the database it will be closed and used for statistical analysis. All data management procedures will be carried out on validated systems and according to the current Standard Operating Procedures (SOPs) of the IMBI.

9.2 Archiving of Essential Documents

The investigator(s) will archive all study data (source data and Investigator Site File (ISF) including subject identification list and relevant correspondence) according to the section 4.9 of the ICH Consolidated Guideline on GCP (E6) and to local law or regulations.

The sponsor or other owner like investigators of the data shall retain all other documentation pertaining to the study for at least 10 years according to the §13 of the German GCP-Ordinance.

Any change of data ownership shall be documented. All data shall be made available if requested by relevant authorities.

TMF (Trial Master File) will be organized by KKS and archived by the coordinating investigator (LKP).

10 ETHICAL AND LEGAL ASPECTS

10.1 Good Clinical Practice

The procedures set out in this study protocol, pertaining to the conduct, evaluation, and documentation of this study, are designed to ensure that all persons involved in the study abide by ICH harmonized tripartite guideline on Good Clinical Practice (ICH-GCP) and the ethical principles described in the applicable version of the Declaration of Helsinki. The study will be carried out in keeping with local legal and regulatory requirements.

10.2 Legal bases

The study has to be conducted in compliance with the protocol, ICH-GCP and the applicable regulatory requirements.

10.2.1 Declaration of Helsinki

The study will be carried out in conformity with the "Ethical principles for medical research involving human subjects" of the 18th World Medical Association General Assembly in Helsinki (1964), and amended by the 29th, 35th, 41st, 48th, 52nd and 59th, World Medical Association General Assemblies (Tokyo 1975, Venice 1983, Hong Kong 1989, Somerset West 1996, Edinburgh 2000, Seoul 2008, and Fortaleza 2013) and the Note of Clarification on Paragraph 29 added by the World Medical Association General Assembly, Washington 2002 and the Note of Clarification on Paragraph 30 added by the WMA General Assembly, Tokyo 2004. The applicable version for the respective country will be taken into consideration.

10.2.2 Other Legal Bases

The other legal bases of this clinical study are as follows:

- ICH Topic E6, Guideline for Good Clinical Practice, including post Step 4 errata, September 1997
- Directive 2001/20/EC (April 4, 2001)
- Commission Directive 2005/28/EC (April 8, 2005)
- National regulatory requirements/guidelines of the participating countries concerning Clinical Studies [e.g. federal drug law (AMG), GCP ordinance (GCP-Verordnung), Medical device law (MPG)]
- General national regulatory requirements, e.g. Bundesdatenschutzgesetz (BDSG)

10.3 Approval of Study Protocol and Amendments

Before the start of the study, the study protocol, informed consent document, and any other appropriate documents will be submitted to the independent Ethics Committee (EC) as well as to the competent authority (BfArM).

A written favorable vote of the EC and an (implicit) approval by the competent authority are a prerequisite for initiation of this clinical study. The statement of EC should contain the title of the study, the study code, the study site, and a list of reviewed documents. It must mention the date on which the decision was made and must be officially signed by a committee member. This documentation must also include a list of members of the EC present on the applicable EC meeting and a GCP compliance statement.

The investigator, supported by the KKS Heidelberg, will keep a record of all communication with the EC and the regulatory authorities.

Before the first subject is enrolled in the study, all ethical and legal requirements must be fulfilled.

All planned substantial changes (see §10, [28] of German GCP-Regulation) will be submitted to EC and the competent authority in writing as protocol amendments. They have to be signed by the sponsor and biometrician and approved by the EC and the competent authority.

10.4 Notification of Regulatory Authorities

In addition to the approval by the competent authority (see 10.3) the clinical study must also be notified to the competent authority before recruitment of the first patient (according to AMG §67).

The local regulatory authorities responsible for each particular investigator will be informed before the beginning, during and at the end of the study according to the applicable regulations. Each investigator is obliged to notify his/her local regulatory authority whereas the notification of the competent authority is the responsibility of the sponsor. Both responsibilities have been delegated to the KKS.

Substantial Amendments, interruption or premature end of the study need to be reported, too.

10.5 Information, Informed Assent and Informed Consent

Before being admitted to the clinical study, the persons having care and custody of the child must consent to participate after the nature, scope, and possible consequences of the clinical study have been explained in a form understandable to him or her. The persons having care and custody of the child must give consent in writing.

Only if the legal guardians have given consent and the disease has been explained to the patient in general, the patient is also informed about the study. The extent and manner of this information depends on the maturity of the child. Signing of the assent form (if the patient is able to write) is considered only as documentation of not having refused study participation. Alternatively, the investigator documents that the child understood the information given and does not refuse participation in the study.

A copy of the signed informed consent document must be given to the persons having care and custody of the child; the original will be filed by the investigator. If the assent form for the child has been signed as well, a copy is given to the patient resp. the legal guardians, too. The documents must specify who informed the patient and the persons having care and custody of the child.

The persons having care and custody of the child will be informed as soon as possible if new information may influence his/her decision to participate in the study. Depending on the maturity of the child, also the child is informed about such news. The communication of this information should be documented.

10.6 Insurance

According to § 40 AMG, the sponsor has to subscribe to an insurance policy covering, in its terms and provisions, its legal liability for injuries caused to participating persons and arising out of this research performed strictly in accordance with the scientific protocol as well as with applicable law and professional standards. The insurance was taken out at Zurich Insurance plc (insurance number: 801.520.894.139).

Any impairment of health which might occur in consequence of study participation must be notified to the insurance company. The subject is responsible for notification. The insured person will agree with all appropriate measures serving for clarification of the cause and the extent of damage as well as the reduction of damage.

During the conduct of the study, the subject must not undergo other clinical treatment except for cases of emergency. The subject is bound to inform the investigator immediately about any

adverse events and additionally drugs taken. The terms and conditions of the insurance should be delivered to the subject.

The insurance company has to be informed about all amendments that could affect subjects' safety.

10.7 Continuous Information to the Ethics Committee and the Competent Authority

Pursuant to the German Drug Law (AMG) and the GCP Ordinance, the responsible EC, the competent authority and all participating investigators will be informed of all suspected serious unexpected adverse reactions (SUSARs) occurring during the study. Both institutions will be informed in case the risk/benefit assessment did change or any others new and significant hazards for subjects' safety or welfare did occur. Furthermore, a report on the subject's safety will be submitted once a year – Development Safety Update Report.

The EC and the regulatory authorities must be informed of the end of the study. They will be provided with a summary of study results within one year after the end of clinical phase (LPO).

11 QUALITY CONTROL AND QUALITY ASSURANCE

The sponsor, the investigators, and all involved study personnel agree to conduct this clinical study in accordance with the ICH Guideline for Good Clinical Practice.

